8.2.6.2. Total Immunoglobulin E (IgE)

Patients with AD often have elevated IgE. Total IgE levels have been found to modestly correlate with AD severity, and may be involved in the pathogenesis of the disease. Changes in total IgE reflects not only on AD, but atopy in general. Baseline IgE levels will be assessed for potential predictive value for treatment response. Post-treatment samples will be evaluated for PD effects of study treatment on total IgE.

Total IgE will be measured in serum from samples collected at time points indicated in [Table 2](#). Detailed instructions for blood sample collection are provided in the study reference manual/site binder or file. Data analysis will be described in the SAP and the results will be described in the CSR.

8.2.6.3. Total Interleukin-33 (IL-33)

Total IL-33 is a measure of target engagement for REGN3500. Total IL-33 will be measured in serum from samples collected at time points indicated in [Table 2](#). Data analysis will be described in the SAP and the results will be described in the CSR.

8.2.6.4. High-Sensitivity C-Reactive Protein (hs-CRP)

C-reactive protein (CRP) is a biomarker of Type 1 inflammation. High-sensitivity CRP, which is more precise than standard CRP, can be used to measure of chronic inflammation or detect low-grade inflammation.

Baseline hs-CRP levels may be assessed for potential predictive value for treatment response. Post-treatment samples may be evaluated for effects of study treatment on hs-CRP. High-sensitivity CRP may be measured in plasma from samples collected at time points indicated in [Table 2](#). Detailed instructions for blood sample collection are provided in the study reference manual/site binder or file. Data analysis will be described in the SAP and the results will be described in the CSR.

8.2.6.5. Serum Amyloid A (SAA)

Serum amyloid A is an early and sensitive blood biomarker for tissue injury and Type 1 inflammation and has been indicated in many inflammatory diseases. The level of SAA circulating in the blood is known to increase dramatically in response to tissue damage or inflammation, classifying it as an acute phase protein

Serum amyloid A may be measured in samples collected at time points indicated in [Table 2](#). Detailed instructions for sample collection are provided in the study reference manual/site binder or file. Data analysis will be described in the SAP and the results will be described in the CSR.

8.2.7. Future Biomedical Research (FBR)

The unused biomarker samples for study-related research, as well as unused PK and ADA samples, will be stored for up to 15 years after the final date of the database lock. The unused samples may be utilized for Future Biomedical Research (FBR) of AD, REGN3500 and its pathway and related diseases. Additional samples will be collected for FBR. After 15 years, any residual samples will be destroyed. The results of these FBR analyses will not be presented in the CSR.

8.2.7.1. Pharmacogenomics Analysis

Whole blood samples for DNA extraction should be collected on day 1/baseline (predose), but can be collected at a later study visit. Whole blood samples for RNA extraction will be collected at time points according to [Table 2](#).

DNA and RNA samples will be collected for the pharmacogenomics analyses to understand the genetic determinants of efficacy and safety associated with the treatments in this study and the molecular basis of AD and related diseases. These samples will be single-coded as defined by the International Council for Harmonisation (ICH) guideline E15. Samples will be stored for up to 15 years after the final date of the database lock. If there are specific site or country requirements involving the pharmacogenomics analyses which the sponsor is unable to comply with, samples will not be collected from patients at the site.

The purpose of the pharmacogenomics analyses is to identify genomic associations with clinical or biomarker response to REGN3500, other AD clinical outcome measures and possible AEs. In addition, associations between genomic variants and prognosis or progression of AD as well as related allergic/atopic diseases may also be studied. These data may be used or combined with data collected from other studies to identify and validate genomic markers related to the study drug or AD and related diseases.

Analyses may include sequence determination or single nucleotide polymorphism studies of candidate genes and surrounding genomic regions. Other methods, including whole-exome sequencing, whole-genome sequencing, DNA copy number variation, and transcriptome sequencing (or other methods for quantitating RNA expression) may also be performed. The list of methods may be expanded to include novel methodology that may be developed during the course of this study or sample storage period. Results from the genomic analyses will not be reported in the CSR.

9. SAFETY DEFINITIONS, REPORTING, AND MONITORING

9.1. Obligations of Investigator

The investigator must promptly report to the Institutional Review Board (IRB)/Ethics Committee (EC) all unanticipated problems involving risks to patients, according to local regulations. This may include death from any cause and all SAEs related to the use of the study drug. It is recommended that all SAEs be reported to the IRB/EC, according to local regulations.

9.2. Obligations of Sponsor

During the course of the study, the sponsor will report in an expedited manner all SAEs that are both unexpected and at least reasonably related to the study drug (ie, SUSAR), to the health authorities, ECs/IRBs as appropriate, and to the investigators (in a blinded manner).

Any AE not listed as an expected event in the Reference Safety Information section of the Investigator's Brochure will be considered as unexpected. Any worsening of or new onset of symptoms related to AD which occur during the screening period prior to study drug administration will be considered expected.

In addition, the sponsor will report in all other SAEs to the health authorities, according to local regulations.

At the completion of the study, the sponsor will report all safety observations made during the conduct of the study in the CSR to health authorities and ECs/IRB as appropriate.

9.3. Definitions

9.3.1. Adverse Event

An AE is any untoward medical occurrence in a patient administered a study drug which may or may not have a causal relationship with the study drug. Therefore, an AE is any unfavorable and unintended sign (including abnormal laboratory finding), symptom, or disease which is temporally associated with the use of a study drug, whether or not considered related to the study drug.

An AE also includes any worsening (ie, any clinically significant change in frequency and/or intensity) of a pre-existing condition that is temporally associated with the use of the study drug.

9.3.2. Serious Adverse Event

An SAE is any untoward medical occurrence that at any dose:

- Results in **death** – includes all deaths, even those that appear to be completely unrelated to study drug (eg, a car accident in which a patient is a passenger).
- Is **life-threatening** – in the view of the investigator, the patient is at immediate risk of death at the time of the event. This does not include an AE that had it occurred in a more severe form, might have caused death.
- Requires in-patient **hospitalization** or **prolongation of existing hospitalization**. In-patient hospitalization is defined as admission to a hospital or an emergency room for longer than 24 hours. Prolongation of existing hospitalization is defined as a hospital stay that is longer than was originally anticipated for the event, or is prolonged due to the development of a new AE as determined by the investigator or treating physician.
- Results in persistent or significant **disability/incapacity** (substantial disruption of one's ability to conduct normal life functions).
- Is a **congenital anomaly/birth defect**
- Is an **important medical event** - Important medical events may not be immediately life-threatening or result in death or hospitalization, but may jeopardize the patient or may require intervention to prevent one of the other serious outcomes listed above (eg, intensive treatment in an emergency room or at home for allergic bronchospasm; blood dyscrasias, or convulsions that do not result in hospitalization; or development of drug dependency or drug abuse).

Criteria for reporting SAEs must be followed for these events. See Section 9.4 for more information on recording and reporting SAEs.

9.3.3. Adverse Events of Special Interest

An AESI (serious or non-serious) is one of scientific and medical concern specific to the sponsor's product or program, for which ongoing monitoring and rapid communication by the investigator to the sponsor can be appropriate. Such an event might warrant further investigation in order to characterize and understand it. Depending on the nature of the event, rapid communication by the study sponsor to other parties (eg, regulators) might also be warranted (Section 9.4.3).

9.4. Recording and Reporting Adverse Events

9.4.1. Adverse Events

The investigator (or designee) will record all AEs that occur from the time the informed consent is signed until the EOS visit. Refer to study reference manual/site binder or file for the procedures to be followed.

Information on follow-up for AEs is provided in Section 9.4.6. Laboratory, vital signs, or ECG abnormalities are to be recorded as AEs as outlined in Section 9.4.5.

9.4.2. Serious Adverse Events

All SAEs, regardless of assessment of causal relationship to study drug, must be reported to the sponsor (or designee) within 24 hours. Refer to the study reference manual/site binder or file for the procedure to be followed.

Information not available at the time of the initial report must be documented in a follow-up report. Substantiating data such as relevant hospital or medical records and diagnostic test reports may also be requested.

In the event the investigator is informed of an SAE after the patient completes the study, the following will apply:

- SAE with an onset within 30 days of the EOS visit or within 140 days of last study drug administration if the patient early terminated from the study - the SAE will be reported to the sponsor. The investigator should make every effort to obtain follow-up information on the outcome until the event is considered chronic and/or stable.
- SAE with an onset day greater than 30 days from the EOS/ET visit - only fatal SAEs and those deemed by the investigator to be drug-related SAEs will be reported to the sponsor. The investigator should make every effort to obtain follow-up information on the outcome of a drug-related SAE until the event is considered chronic and/or stable.

9.4.3. Other Events that Require Accelerated Reporting to Sponsor

The following events also require reporting to the sponsor (or designee) within 24 hours of learning of the event:

Symptomatic Overdose of Study Drug: Accidental or intentional overdose of at least 2 times the intended dose of study drug within the intended therapeutic window, if associated with an AE,

Pregnancy: Although pregnancy is not considered an AE, it is the responsibility of the investigator to report to the sponsor (or designee), within 24 hours of identification, any pregnancy occurring in a female during the study or within 140 days of the last dose of study drug. Any complication of pregnancy affecting a female study patient and/or fetus and/or newborn that meets the SAE criteria must be reported as an SAE. Outcome for all pregnancies should be reported to the sponsor.

Adverse Events of Special Interest: All AESI, serious and non-serious, must be reported within 24 hours of identification using the same reporting process as for SAE reporting, per Section 9.4.2. Adverse events of special interest for this study include the following:

- Anaphylactic reactions or acute allergic reactions that require immediate treatment
- Severe ISRs that last longer than 24 hours
- Mycosis fungoides or other forms of cutaneous T-cell lymphoma
- Any severe infection; any infection requiring treatment with parenteral antibiotics/anti-viral/anti-fungal agent; any infection requiring treatment with oral antibiotic/anti-viral/anti-fungal for longer than 2 weeks; any clinical endoparasitosis; any opportunistic infection

Note:

Generally, all uncommon, atypical, peculiar, or unusually persistent infections, especially viral infections, should be reported as AESIs.

- Conjunctivitis (any type or etiology), keratitis, or blepharitis (only events that are either severe or serious or lasting ≥ 4 weeks will be reported as AESIs)

Any patient who experiences an AESI related to an eye disorder will be referred to an ophthalmologist. Further evaluation of these AESIs will be performed including any additional tests, as per the discretion of the ophthalmologist.

- Significant ALT elevation
 - ALT $>3 \times$ ULN associated with total bilirubin $>2 \times$ ULN; or
 - ALT $>5 \times$ ULN in patients with baseline ALT $\leq 2 \times$ ULN; or
 - ALT $>8 \times$ ULN if baseline ALT $>2 \times$ ULN

Refer to the study reference manual/site binder or file for the procedures to be followed.

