4.2.2. Secondary Endpoints

The secondary endpoints are:

Efficacy:

- Proportion of patients achieving EASI-50, EASI-75, and EASI-90 ($\geq 50\%$, $\geq 75\%$, and $\geq 90\%$ improvement from baseline) at week 16
- Absolute change in EASI scores from baseline to week 16
- Proportion of patients with both an IGA score of 0 or 1 (on a 5-point scale) and a reduction from baseline of ≥ 2 points at week 16
- Change (absolute and percent) from baseline to week 16 in weekly average of daily peak Pruritus Numerical Rating Scale (NRS)
- Proportion of patients with improvement (reduction) of weekly average of daily peak Pruritus NRS ≥ 4 from baseline to week 16
- Time to onset of effect on pruritus during the 16-week treatment period (≥ 4 -point reduction of weekly average of daily peak Pruritus NRS from baseline)
- Percent change from baseline to week 16 in SCORing Atopic Dermatitis (SCORAD)
- Change from baseline to week 16 in percent BSA of AD involvement

Safety:

- Incidence of treatment-emergent adverse events (TEAEs) from baseline through end of treatment (week 16)
- Incidence of treatment-emergent serious adverse events (SAEs) from baseline through end of treatment (week 16)
- Incidence of treatment-emergent adverse events of special interest (AESIs) from baseline through end of treatment (week 16)
- Incidence of TEAEs from baseline through end of study (week 36)
- Incidence of treatment-emergent SAEs from baseline through end of study (week 36)
- Incidence of treatment-emergent AESIs from baseline through end of study (week 36)

Pharmacokinetic:

- Concentrations of functional REGN3500 in serum by treatment regimen at each assessment timepoint from baseline to end of study (week 36)

Any exploratory endpoints will be described in the statistical analysis plan (SAP).

Note: The safety and PK endpoints will not be included in the testing hierarchy.

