10.4.4.1. Adverse Events

Definitions

For safety variables, 2 observation periods are defined:

- The pretreatment period is defined as the time from signing the ICF to before the first dose of study drug.
- The treatment-emergent period is defined as the day from first dose of study drug to the end of study. The treatment-emergent period includes the 16-week treatment period and follow-up period.
 - Treatment period: date of the first dose of study drug to week 16 visit date (study day 113 starting from the first dose of study drug if week 16 visit date is unavailable) or ET date, whichever comes first.
 - Follow-up period: date after week 16 visit date (study day 113 starting from first dose of study drug if week 16 visit date is unavailable) to EOS visit.

Treatment-emergent AEs are defined as those that are not present at baseline or represent the exacerbation of a pre-existing condition during the treatment-emergent period.

Analysis

All AEs reported in this study will be coded using the currently available version of the Medical Dictionary for Regulatory Activities (MedDRA[®]). Coding will be to lowest level terms. The verbatim text, the preferred term (PT), and the primary system organ class (SOC) will be listed.

Summaries of all TEAEs by treatment group and for overall during the treatment-emergent period, during the 16-week treatment period, and during the follow-up period will include:

- The number (n) and percentage (%) of patients with at least 1 TEAE by SOC and PT
- TEAEs by severity (according to the grading scale outlined in Section 9.5.1), presented by SOC and PT
- TEAEs by relationship to treatment (related, not related), presented by SOC and PT
- Treatment-emergent AESIs (defined with a PT or a prespecified grouping)

Deaths and other SAEs will be listed and summarized by treatment group.

Treatment-emergent AEs leading to permanent treatment discontinuation will be listed and summarized by treatment group.

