4.6.2. Adverse Events of Special Interest

In this study, the adverse event of special interest (AESI) category includes:

- Anaphylactic reactions or acute allergic reactions that require immediate treatment
- Severe ISRs that last longer than 24 hours
- Mycosis fungoides or other forms of cutaneous T-cell lymphoma
- Any severe infection; any infection requiring treatment with parenteral antibiotics/anti-viral/anti-fungal agent; any infection requiring treatment with oral antibiotic/anti-viral/anti-fungal for longer than 2 weeks; any clinical endoparasitosis; any opportunistic infection
- Conjunctivitis (any type or etiology), keratitis, or blepharitis (only events that are either severe or serious or lasting ≥ 4 weeks will be reported as AESIs)

- Significant ALT elevation
 - a. ALT >3×ULN associated with total bilirubin >2×ULN; or
 - b. ALT >5×ULN in patients with baseline ALT ≤2×ULN; or
 - c. ALT >8×ULN if baseline ALT >2×ULN

The search criteria for AESIs are provided in Section 10.4.

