5.8.2. Analysis of Adverse Events of Special Interest

The adverse events of special interest (AESI) will be summarized by AESI category (see Section 10.4) and by high level term and PT.

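### The SAP's AESI list and search omit the protocol's class of unusual or persistent infections and ignore investigator-reported AESIs, so some such events reach the AESI summary only through an optional review

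*Protocol*

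**What the plan says.** Protocol 9.4.3 lists the AESIs for the study. Beneath the infection entry it adds: "Generally, all uncommon, atypical, peculiar, or unusually persistent infections, especially viral infections, should be reported as AESIs". It also sets the reporting route: "All AESI, serious and non-serious, must be reported within 24 hours of identification using the same reporting process as for SAE reporting". Protocol 4.2.2 makes the incidence of treatment-emergent AESIs a secondary safety endpoint twice, once to week 16 and once to week 36.

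SAP 4.6.2 reproduces the infection entry down to "any clinical endoparasitosis; any opportunistic infection" and stops there; the note is missing. It then says: "The search criteria for AESIs are provided in Section 10.4". SAP 5.8.2 gives the analysis: "The adverse events of special interest (AESI) will be summarized by AESI category (see Section 10.4) and by high level term and PT".

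SAP 10.4 opens by admitting that its criteria may be neither exhaustive nor specific. It allows, without requiring, a blinded review of all preferred terms by the medical monitor to add events the search missed or remove events it wrongly included.

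**The concern.** Collection and analysis work from different definitions of one endpoint. Sites are told to treat an unusual or unusually persistent infection as an AESI and to send it to the sponsor by the accelerated route. The SAP then finds AESIs through a search that has no category for such an infection and does not consult the site's report. An event that the sponsor received as an AESI could therefore be missing from the AESI table.

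What is at stake is the completeness of a secondary safety endpoint. The study was stopped early and all analyses are descriptive, but SAP 1.1 says that development of the drug continues in other diseases, so its safety tables keep their use.

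**Working it through.** The plan gives no figure on this point and no arithmetic applies. The check compares the class in the protocol's note with each relevant search row in SAP 10.4.

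| SAP 10.4 row | What the search requires | Part of the note's class that it catches |
|---|---|---|
| Severe infection | Infections SOC, and severe or serious | Only severe or serious cases |
| Parenteral treatment | Infections SOC, medication given, anti-infective by IV or IM route during the event | Only cases treated that way |
| Prolonged oral treatment | Infections SOC, medication given, one of two antibacterial ATC classes (penicillins, other antibacterials), oral, over 14 days | Only cases on those antibacterials |
| Endoparasitosis | Four HLTs for worm infections | Worm infections only |
| Opportunistic infection | Listed HLTs and PTs, some starred for manual adjudication | Listed terms only, including the whole herpes viral HLT with no severity, seriousness or duration condition |
| Eye rows | Conjunctivitis and blepharitis terms if severe, serious or lasting at least 4 weeks; listed keratitis PTs | Infective eye conditions only |

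Three results follow.

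1. No row is defined by an unusual nature or an unusually long course, and no row or accompanying text in SAP 10.4 uses the investigator's AESI report.

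2. The prolonged-oral row does not match its own title. The title covers antibiotics, antivirals and antifungals; the search names antibacterial classes only. This affects an entry that SAP 4.6.2 does carry over, not just the missing note.

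3. Some protocol-defined AESIs meet no row. Take a viral infection that is moderate, non-serious, unusually persistent, not in the eye, and outside the herpes HLT and the listed viral PTs.
   - If it is given an oral antiviral for more than 14 days, it is an AESI under the explicit oral-treatment entry and under the note. It fails the severe row, the parenteral row, the antibacterial-only oral row and both term lists.
   - If it is given no systemic treatment, it is an AESI under the note alone, and again no row finds it.

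The remaining route is the review of preferred terms. SAP 10.4 says only that it *may* take place, whereas for anaphylaxis, conjunctivitis, keratitis and the starred opportunistic terms the same section makes manual adjudication a requirement. The review also works from preferred terms. A preferred term names the infection; it does not show that the course was atypical or prolonged. No rule tells the reviewer to apply the protocol's note. The site's AESI report carries that judgement, and the SAP does not use it.

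**The case against.** The strongest reply is that the SAP follows the protocol's own analysis definition. Protocol 10.4.4.1 summarizes "Treatment-emergent AESIs (defined with a PT or a prespecified grouping"), with no mention of an investigator flag. The note itself is hedged, and words such as peculiar or atypical match no preferred term, so medical review is the natural means of capture, and SAP 10.4 provides for one. This stands in part: a search-based approach is permitted. But it requires a grouping to be prespecified, none exists for this class, and the review is optional.

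Other replies stand.

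- The events are not lost. SAP 4.6.1 counts every AE collected in treatment and follow-up as a TEAE, and SAP 5.8.1 tabulates TEAEs by SOC, HLT, PT, severity and relatedness. SAP 4.6.1 also requires blinded adjudication of infection and skin TEAEs, though to identify skin infections, not to assign AESI status.
- A reader might infer that the SAP's definition can only lower the infection AESI count. The documents do not support this. SAP 10.4 is wider than the protocol in places: it adds serious but non-severe infections to the severe row, and it takes in the whole herpes HLT unconditionally. The net direction is undetermined.
- A reader might infer an undeclared change because SAP 1.2.4 does not list the omission. That section covers changes to the protocol's statistical section; the note sits in the safety-reporting section, so its absence there shows nothing.
- The documents do not show whether the CRF holds an AESI field, so the ease of a merge cannot be taken for granted.

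**Conclusion.** The concern holds in a limited form. The AESI set that the SAP specifies leaves out a class that the protocol tells sites to report. Infections in that class that are non-severe, non-serious, off the listed terms and without qualifying treatment enter the AESI summary only if the optional review adds them. The antibacterial-only oral search opens a second gap, in an entry that both documents share.

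A reader might conclude that such infections are simply absent from the AESI endpoint. That goes too far: the rows for severe or serious, parenterally treated, opportunistic and eye events catch part of the class, and the optional review could add more. They can be absent; they need not be.

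The size cannot be stated. The documents give no rate of unusual infections, the search applies equally to the placebo arm, and the number of missed events may be zero. Any per-arm percentage would be a guess. No hypothesis is tested, so no error rate is affected. The conclusion rests on the text of SAP 4.6.2, 5.8.2 and 10.4 as written, and assumes that no unseen document makes the review mandatory or brings in the site reports. It is a gap in prespecification that should be closed, because the endpoint as analysed may not match the endpoint as collected.

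**What to change.** Three changes to the SAP:

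1. Restore the note from Protocol 9.4.3 to the infection entry in SAP 4.6.2.
2. In SAP 5.8.2 and 10.4, define the AESI set as events found by the search criteria plus events that investigators reported as AESIs under Protocol 9.4.3. Require a blinded medical-monitor reconciliation of the two sources before database lock, with the monitor assigning the category.
3. Add antiviral and antifungal classes to the prolonged-oral-treatment search so that it matches its title.

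The cost is SAP wording, an extended medication search and a small amount of extra blinded review. No new data collection should be needed: AESI reports already go to the sponsor by the SAE process, and Protocol 11.2 lists a pharmacovigilance safety database. If the CRF has no AESI field, the reconciliation would have to draw on the accelerated reports themselves.
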